NCT03705273

Randomized controlled trial of dexamethasone
oral preparations to assess palatability and adverse effects
in children with asthma and croup

Protocol Date: 09.19.2018

Study Description and Protocol

Principal Investigator:
[name], MPH
Pediatric Emergency Medicine

Co-investigators
[name].
Pediatric Pharmacy Resident

[name]., BCPPS
Pediatric Clinical Pharmacist

[name]., BCPS, BCPPS
Pediatric Clinical Pharmacist

Vanderbilt Children's Hospital
[name]
[name]

09.19.18

I. Specific Aim and Study Hypothesis

Specific Aim: To examine the palatability and acceptability of oral dexamethasone tablets crushed in apple sauce or pudding in comparison with the IV solution mixed with sugar syrup.

Hypothesis: We hypothesize that dexamethasone tablets crushed and administered in apple sauce or pudding at a dose of 0.6 mg/kg will be more palatable and acceptable in comparison to the IV form of the drug mixed in sugar syrup, for acute asthma exacerbations or croup in children aged 1 – 7 years in a pediatric emergency department.

II. Summary of Approach

To address the Specific Aim we will conduct a 2-arm RCT of dexamethasone tablets crushed in apple sauce or pudding in comparison to the current approach in the VCH ED, dexamethasone IV solution mixed in sugar syrup. The outcome, palatability and acceptability, will be assessed using a smiley-face analog scale and questionnaire that will be completed by the participant's parent 1-hour after administration of dexamethasone.

Treatment allocation (randomization) will be determined by a pre-determined randomization sequence in randomly-permuted blocks of 4, to be generated using Stata statistical software. Envelopes containing treatment allocation by sequential participant ID will be in the VCH-ED charting room where physicians and nurse practitioners enter orders for this medication in Epic. When a parent and patient provide consent/assent, the next envelope will be opened to determine treatment allocation. The clinician will then enter the order for dexamethasone tablets or IV solution in accordance with this. The clinician will ask the participant's parent to complete the data collection form (enclosed with this application) 1-hour after medication administration.

Treatment allocation cannot be blinded because the vehicle (apple sauce, pudding or sugar syrup) may be associated with palatability and acceptability.

III. Background

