Asthma is the most prevalent chronic serious disease of childhood and the most frequent reason for childhood hospitalization in the United States. Asthma and croup are common patient diagnoses in the pediatric emergency department, and national guidelines recommend oral dexamethasone (a corticosteroid) as a fundamental treatment for both conditions. Dexamethasone is the preferred corticosteroid because the duration of clinical effect is 2-3 days, a period sufficient to treat these conditions. The current dexamethasone preparation used at VCH is the intravenous (IV) preparation mixed with cherry syrup. Our nursing staff prefers this preparation. However, some children spit this preparation out or have vomiting afterward.

IV. Inclusion and Exclusion Criteria

a. Inclusion criteria

- i. Diagnosis of acute asthma exacerbation or croup (laryngotracheitis) in the VCH ED
- ii. Age 1 to 7 years
- iii. Dexamethasone treatment indicated
- iv. No other acute or chronic process accounting for signs and symptoms (e.g., foreign body aspiration, pneumonia, cystic fibrosis)
- v. Have not received systemic corticosteroid for current episode prior to enrollment

b. Exclusion criteria

- i. Allergy to dexamethasone or apple sauce and pudding
- ii. Unable to take medication orally

V. Subject Recruitment and Enrollment

We will enroll a convenience sample of 220 children 1-7 years of age and their parent, who will provide secondary data on their child. The investigators will be clinicians (attending physicians, fellows, pharmacists, nurses, or nurse practitioners) caring for patients in the VCH ED and will identify patients presenting with signs (e.g., tachypnea, wheezing, accessory muscle use) and symptoms (e.g., respiratory distress, dyspnea, cough,) consistent with an asthma exacerbation or croup (barky cough, inspiratory stridor).

The investigator will seek written informed consent from the parent and verbal assent from the child. If these are provided, the patient will be enrolled as a participant. Based on the proposed sample size described in a later section of the protocol, we anticipate enrollment of 220 patients and 220 parents.

VI. Study Procedures

Study Design

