The study design will be an RCT with randomization in randomly-permuted blocks of four. After participant enrollment and ascertainment of treatment allocation (randomization), the clinician will order dexamethasone accordingly in tablet or IV form. The investigator will provide the parent with the study data form and instruct the parent in completion of this form 1-hour after dexamethasone administration.

VII. Predictor Variables

The predictor variable will be treatment-allocation (dexamethasone tablet or IV preparation administered orally).

VIII. Outcome Variables

The outcome variable will be palatability as defined by a 5-point "smiley-face" visual analog scale that the parent will complete on the study data form. Secondary outcomes will include emesis; need to re-administer the medication, need to provide alternate vehicle for medication (e.g., intravenous or intramuscular).

IX. Ethical Considerations

Systemic corticosteroid is a fundamental component of treatment for acute asthma exacerbations and croup, and dexamethasone has been identified at VCH and nationally as the optimal systemic corticosteroid for these children. The IV form of dexamethasone is used currently at VCH and in most pediatric ED's nationally. However, previous research has demonstrated that dexamethasone tablets are better tolerated than prednisolone (a different corticosteroid) syrup. There is equipoise whether dexamethasone as the IV form or tablet is more palatable and acceptable to these children, and this research seeks to answer the important question whether we should be using the tablets.

X. Risks of Study Participation

The risk to participants is not increased over current practice pertaining to administration of dexamethasone orally. The IV form is currently in use, and the tablets are widely acknowledged to be well tolerated by children. However, any apparent adverse events (e.g., allergy to apple sauce or pudding) will be reported by the investigators to [name] who will immediately inform the IRB as noted below.

XI. Reporting of Adverse Events or Unanticipated Problems Involving Risk to Subjects or Others

Any unexpected problems involving risks to subjects or others will be immediately reported to the Institutional Review Board of Vanderbilt University within ten days using the IRB form #1105.

XII. Study Withdrawal or Discontinuation

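### Does Section VIII need a named acceptability outcome, and spitting out as a listed event, because the hypothesis says the tablets will be more acceptable?

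*Combined protocol and SAP*

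**What the plan says.** Section I hypothesises that the tablets "will be more palatable and acceptable in comparison to the IV form of the drug mixed in sugar syrup". Section II keeps both terms and names the instruments: "The outcome, palatability and acceptability, will be assessed using a smiley-face analog scale and questionnaire". The clinician asks the "parent to complete the data collection form (enclosed with this application) 1-hour after medication administration". Section IX repeats the pair: "There is equipoise whether dexamethasone as the IV form or tablet is more palatable and acceptable to these children".

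Section III gives the motive for the trial. With the current preparation, "some children spit this preparation out or have vomiting afterward".

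Section VIII is narrower. It begins "The outcome variable will be palatability as defined by a 5-point" smiley-face scale and continues: "Secondary outcomes will include emesis; need to re-administer the medication, need to provide alternate vehicle for medication (e.g., intravenous or intramuscular". Section XV describes how the parent's mark on the scale becomes a continuous palatability score, and Section XVI sizes the trial on that score. Neither mentions acceptability or sets out a test for any secondary outcome.

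**The concern.** Read alone, Section VIII drops a construct that the aim, the hypothesis and the equipoise statement all carry. A reader cannot tell from it which result would support a claim that the tablets are more acceptable. In principle, that claim could be attached afterwards to whichever item came out well.

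The omission of spitting out makes this sharper. Section III names two faults of the current preparation. Vomiting became an outcome and spitting out did not. As listed, a spat-out dose counts only if it leads to a repeat dose or a different means of giving the drug. Those are staff decisions in a trial of which Section II says: "Treatment allocation cannot be blinded because the vehicle (apple sauce, pudding or sugar syrup) may be associated with palatability and acceptability".

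There is also a small question of wording. Section II uses the word vehicle for the food or syrup that carries the drug, whereas the examples in Section VIII are routes of administration.

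**Working it through.** **1. Is the primary comparison affected?** Section XVI gives a difference of 0.5, SD 1.1, power 0.9 and alpha 0.05. The normal approximation, two-sided, is

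n = 2 × (1.960 + 1.282)² × 1.1² / 0.5² ≈ 101.7, so 102 per arm.

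The two-sample t-test gives 102.68, so 103 per arm, which is the plan's figure. Enrolling 110 per arm allows for 1 − 206/220 = 6.4% loss. All of this rests on palatability alone, so how acceptability is labelled does not enter it.

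**2. Where each construct appears.**

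| Section | Palatability | Acceptability |
|---|---|---|
| I (aim, hypothesis) | yes | yes |
| II (approach) | smiley-face scale and questionnaire, named jointly for both | same instruments |
| VIII (outcomes) | primary outcome | no outcome given this label |
| IX (equipoise) | yes | yes |
| XV, XVI | analysed and sized | not mentioned |

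Acceptability has an instrument (Section II) but no label in Section VIII. The questionnaire items are on a form outside the public text. Their absence there does not show that they are missing from the study.

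**3. What happens to a spat-out dose.**
- It is followed by a repeat dose: counted as re-administration.
- It is followed by another means of giving the drug: counted as alternate vehicle. The routes in that item are introduced as examples, so a change of oral vehicle is not excluded.
- No action follows: not a listed event, unless the form asks about it or the list, which is worded as open-ended, is read to cover it.

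Only the third path is open. The documents give no rate for spit-out, so the share of spit-outs on that path could be anything from 0 to 100%.

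**4. What a separate spit-out outcome would add.** All rates here are assumptions. The 95% CI half-width is 1.96 × √[p₁(1−p₁)/n + p₂(1−p₂)/n] with n = 103. For 20% v 10%, this is 1.96 × √[(0.16 + 0.09)/103] = 1.96 × 0.0493 = 9.7 points. Power is from exact binomial enumeration of the two-sided pooled z-test at 0.05.

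| Assumed rates | 95% CI half-width | Power |
|---|---|---|
| 10% v 5% | 7.2 points | 0.28 |
| 15% v 5% | 8.1 points | 0.70 |
| 20% v 10% | 9.7 points | 0.53 |
| 25% v 10% | 10.2 points | 0.82 |

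These figures describe the possible addition. They do not measure a loss in the plan as it stands.

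**5. Multiplicity.** If every secondary outcome were tested at 0.05 and the tests were independent, the chance of at least one false positive would be 1 − 0.95³ = 0.143 with three outcomes and 1 − 0.95⁴ = 0.185 with four. Spit-out and repeat dosing would probably be positively correlated, which would bring the second figure below 0.185. Section XV specifies no such tests, so this is hypothetical.

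**The case for a change.** The best argument for a change is that it is cheap and the mismatch is real. Sections I, II and IX promise a conclusion on acceptability, and Section VIII names no variable that decides it. An open-ended list does not prespecify one, and re-administration is only a partial stand-in for spitting out. A sentence in Section VIII, and perhaps a tick box on the form, would close the gap without adding a participant.

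The mismatch stands: the link between the questionnaire and acceptability is not carried from Section II into Section VIII. The rest is weaker.

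- The risk of choosing a favourable item afterwards depends on what the form contains, and the text does not show that.
- A problem mentioned in the background need not become an outcome of its own. Counting only spit-outs that staff act on is a defensible choice.
- The added item would not remove the bias complained of. Staff know the allocation when they decide whether to repeat a dose, but the parent who would tick the box knows it too. A partial spit-out would also need a threshold.
- Reporting the listed components separately, and wording the conclusion to match, is as legitimate as nominating one deciding variable.

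**Conclusion.** No change to the plan follows. Section VIII leaves a label unwritten. It does not state a rule that gives a wrong answer. The primary analysis and the 103 per arm reproduce and are unaffected.

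The possible loss on the secondary side cannot be sized, because it depends on unreported rates and on a form that is not in the public text. The extra outcome would be unblinded like the others. Under the assumed rates, its power exceeds 0.8 only for 25% v 10%.

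The gap is one that analysts fill sensibly: report the questionnaire items and the three listed events by arm, and tie any statement about acceptability to the variable it rests on. This rests on two assumptions: that the enclosed form carries the questionnaire Section II describes, and that the report does not claim superior acceptability without saying what was measured. If the form proved to contain nothing on acceptability, the claim would have to be limited to palatability and the listed events. The palatability result would still stand.

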We are taking several measures to ensure that there is a clear distinction for the patient and parent/guardian(s) between clinical care and the research data collection for this investigation. Patients and their parent/guardian(s) will be told very explicitly by the investigators that their participation in this research investigation is entirely voluntary and that they may withdraw at any time. We will further emphasize verbally and in the informed consent document that a decision on the part of the patient or parent/guardian(s) to not participate will in no way change, compromise or jeopardize the patient's care. Indeed, we anticipate that some eligible patients will not be enrolled on this basis.

XIII. Data Management

A *Subject Data Form* will be used for data acquisition. All data will be entered in a secure REDCap database. This data will then be entered into Stata® (v.8, College Station, TX) for statistical analysis.

XIV. Clinicaltrials.gov registration: Pending

XV. Statistical Considerations

We will examine palatability using the 5-point analog ("smiley-face") scale and will ask the parent to make a mark on this scale. This mark will be used to estimate palatability as a continuous variable (e.g., 5.6 cm).

XVI. Sample Size

In a cohort of children aged 2 – 10 years who received oral dexamethasone as the elixir and using a 5-point Hedonic scale ("smiley-face" scale) was used to assess palatability,¹ Aljebab and colleagues reported a mean value for palatability of 3 with SD 1.1. If the true, mean difference between dexamethasone tablet and IV solution administered orally is 0.5, we will need to study 103 experimental subjects and 103 control subjects to be able to reject the null hypothesis that the population means of the experimental and control groups are equal with probability (power) 0.9. The Type I error probability associated with this test of this null hypothesis is 0.05.

With the above in mind, we propose to enroll 110 participants in each treatment-allocation arm of this RCT to account for dropouts and missing data.

XVII. Privacy and Confidentiality Issues

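### Does the 90% power still apply when palatability is planned in points of a 5-point scale but read off in centimetres?

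*Combined protocol and SAP*

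**What the plan says.** Section VIII of the protocol names the outcome: "The outcome variable will be palatability as defined by a 5-point" smiley-face visual analog scale, which the parent completes on the study data form. Section XV says that the investigators "will ask the parent to make a mark on this scale", and continues: "This mark will be used to estimate palatability as a continuous variable (e.g., 5.6 cm").

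Section XVI takes its planning values from a published cohort of children given oral dexamethasone and scored on a 5-point face scale. That study "reported a mean value for palatability of 3 with SD 1.1". The target follows directly: "If the true, mean difference between dexamethasone tablet and IV solution administered orally is 0.5", then 103 children are needed in each arm to reject equality of the means "with probability (power) 0.9" at a Type I error of 0.05. Enrolment is set at 110 per arm to cover dropouts and missing data.

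The 0.5 carries no printed unit. It stands next to a mean of 3 and an SD of 1.1 on a 5-point scale, so the natural reading is points. The visible text gives no length for the printed line and no rule linking centimetres to points. Section II says that the data collection form was enclosed with the application; that form is not part of the public text.

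**The concern.** A value of 5.6 cannot be a score on a 1-to-5 scale, so the analysed variable is evidently a length, while the sample size was worked out from scores. Nothing visible links the two. If the analysed variable and the planning variable really were different quantities, the 90% power would describe a variable that nobody analyses, and the 0.5 would not help in judging a result reported in centimetres.

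The worry becomes sharp if 0.5 is read as 0.5 cm. On a line several centimetres long, 0.5 cm is a smaller effect than half a point, and a trial of 103 per arm could be badly underpowered for it. This is also the only outcome that the protocol does not label secondary, so an ambiguity in its unit deserves a check.

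**Working it through.** **Inputs.** Difference 0.5, SD 1.1, power 0.9, Type I error 0.05, 103 evaluable per arm (all from Section XVI). Sidedness is not stated. Two-sided is inferred, because it reproduces the plan's figure and a one-sided calculation gives 83 per arm. Line length L is not in the documents, so 6, 8 and 10 cm are assumed for illustration.

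**Step 1: reproduce the plan.** The normal approximation is n = 2 × [SD × (z₀.₉₇₅ + z₀.₉₀) / difference]² = 2 × [1.1 × (1.960 + 1.282) / 0.5]² = 101.7 per arm. The two-sample t-test at standardised difference 0.5/1.1 = 0.4545 gives 102.7, hence 103, which matches the plan. Power at 103 per arm is 90.1%.

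**Step 2: convert points to centimetres.** Let X be the response in points and Y = a + kX the same response in centimetres. The difference in means becomes k × 0.5, the SD becomes k × 1.1, and a cancels. The ratio is (k × 0.5)/(k × 1.1) = 0.4545 for every k. With five evenly spaced faces and the end faces at the ends of the line, k = L/4:

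| Line L (assumed) | Difference, cm | SD, cm | Ratio | Power at 103 per arm |
|---|---|---|---|---|
| 6 cm | 0.75 | 1.65 | 0.4545 | 90.1% |
| 8 cm | 1.00 | 2.20 | 0.4545 | 90.1% |
| 10 cm | 1.25 | 2.75 | 0.4545 | 90.1% |

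The same holds for the data. A t-test on raw centimetres and a t-test on 1 + 4 × (distance from the worst end / L) give the same t statistic and p-value, because the second variable is a linear function of the first. Rescaling before analysis is therefore not needed to keep the 90%.

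**Step 3: where the low powers come from.** They need the SD in centimetres and the difference held at 0.5 cm. With k = L/4, the ratios are 0.5/1.65 = 0.303, 0.5/2.2 = 0.227 and 0.5/2.75 = 0.182. Power is then 58%, 37% and 25%, and 90% power would need about 230, 408 and 637 per arm. With k = L/5, power is 77%, 53% and 37%. Each of these converts one of the two planning values and not the other. Section XVI gives the two together, from one scale.

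**Step 4: what a unit conversion cannot settle.** The spread of a freely placed mark, expressed in point-equivalents, might not be 1.1. Holding the difference at 0.5 point with 103 per arm:

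| SD in point-equivalents (assumed) | Power | n per arm for 90% |
|---|---|---|
| 0.9 | 97.8% | 70 |
| 1.0 | 94.6% | 86 |
| 1.1 | 90.1% | 103 |
| 1.2 | 84.5% | 123 |
| 1.3 | 78.4% | 144 |

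The departure could go either way. It is the usual uncertainty in borrowing an SD from another study, and restating the unit would not remove it.

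**The case for a change.** The strongest case for a change is that the unit of the main outcome should not be left to inference. Two analysts could report different numbers, one a 1-to-5 score and the other centimetres. A reader who set a result in centimetres against the planned 0.5 would misjudge it: on an assumed 10 cm line with k = 10/4, half a point is 1.25 cm, a factor of 2.5. A result in centimetres also cannot be set directly beside the cited cohort's mean of 3. Since the 0.5 has no printed unit, the reading of 0.5 cm is not strictly excluded, and settling it would cost only a few words.

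Part of this stands. A stated line length and scoring rule would make the estimate easier to read. But the two analysts would reach the same test result, and either could convert the other's estimate from the line length on the form. The comparison with the cohort is peripheral, since the trial compares two randomised arms and the cohort supplies planning values only. The 0.5 cm reading requires the difference to be in another unit than the SD from which it was planned. Nor does the 5.6 cm example prove that a point differs from a centimetre: faces at 1 to 5 cm on a 6 cm strip would also allow a mark at 5.6 cm.

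Writing in one particular conversion could even do harm without sight of the form. The formula 1 + 4 × (distance/L) assumes that the end faces sit at the ends of the line. If the faces sit at the centres of five equal segments, the matching formula is 0.5 + 5 × (distance/L).

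**Conclusion.** The concern does not call for a change. The mismatch in wording is real, but it does not touch the sample size: 103 per arm and about 90% power hold in points and in centimetres alike, because both rest on the ratio 0.4545. Powers of 25% to 77%, and samples of 230 to 637 per arm, describe a 0.5 cm target that the plan does not set. Rescaling the marks, or restating the difference and SD in centimetres, would leave the test statistic, p-value, power and sample size as they are.

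The conclusion assumes that 0.5 is in points, as its context indicates; that the faces are evenly spaced, so that the conversion is linear; and that the means are compared by a two-sided two-sample test, as Section XVI implies. It also inherits the plan's assumption that the marks have an SD near 1.1 in point-equivalents, which the documents cannot confirm. What is left is a scoring detail that an analyst fills sensibly by reporting the line length with the estimate, or by giving the difference in point-equivalents as well.
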